Implants made from oriented poly L-lactide-co-glycolide (PLGA) copolymers are strong enough to support fractured bones. The monomers of PLGA are L-lactic acid and glycolic acid, which are part of the normal metabolic chemistry of human cells. PLGA implants undergo a controlled degradation through hydrolysis forming lactic acid and glycolic acid which are absorbed by the cells and metabolized into carbon dioxide and water. The implant retains strength and size for at least eight weeks and over the course of approximately two years the implant will be completely absorbed [28]. Medical grade PLGA implants manufactured by Bioretec Ltd. ([name]) are sterilized with gamma radiation. Gamma radiation also reduces molecular weight of oriented PLGA implants. The reliability and safety of the Activa IM-Nail[™] has been described in the manufacturer's premarket trials and one RCT [7], the implant is FDA and CE approved for the same purpose as in the present study.

Objectives

Primary objective

The primary objective of this study is to evaluate the amount of radiological healing three months after surgery with the Activa IM-Nail[™] for pediatric diaphyseal forearm fractures.

Secondary objectives

The secondary objectives are to report the functional outcome, calculate refracture rate and any other complications up to two years following surgery and to describe MRI findings two years after insertion of Activa IM-Nail™.

Hypothesis

We hypothesize that radiological healing is established three months after surgery with the Activa IM-Nail™.

Methods and materials

Study design

We use a cohort study design [29] conformed to the STROBE Statement [30]. We aim to recruit all children with diaphyseal forearm fractures (cohort) operated with BIN (exposure) and report radiological healing

(outcome). This study design is relevant in reporting radiological healing and calculating absolute risk of adverse events based on the exposure in our cohort.

Selection and withdrawal of participants

Setting

The study will be performed in the Capital Region of Denmark, Europe. Patients in Herlev and Gentofte University Hospital's catchment area (population 700.000 of which 80.000 are children age 3-15) are eligible for recruitment.

Participants

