Children are not able to give informed consent to participate in a study. Therefore, all legal guardians are asked to consent on behalf of the child. Oral and written information about the study, together with general information about participating in a research project from the Danish National Committee on Health Research Ethics is given face-to-face by the PI prior to asking for consent. Information is given in an undisturbed environment at the pediatric ward. The PI is the head of pediatric orthopedic trauma and is very skilled in communication with both parents and injured children.

Unstable or displaced diaphyseal forearm fractures usually do not require emergent treatment, but we strive to treat fractures as soon as possible. In planning, both surgeons and operating personnel need time to prepare for the specific procedure. Therefore, we ask that consent is given the day before surgery at the latest. Parents will in most cases have at least 24 hours to consider enrollment however, there might be factors (e.g. open fracture or neurovascular compromise) that dictate more emergent treatment requiring consent with less consideration time.

If participation is declined the patient will receive standard treatment with TEN, and standard rehabilitation and follow-up after 2 and 6 weeks and 6 months. TEN will be removed approximately 6 months after insertion during a scheduled outpatient operation under general anesthesia.

Follow-up

Outpatient visits are scheduled at 2 and 6 weeks, 3 and 6 months and 1 and 2 years following surgery.

All participants live in the catchment area of our hospital with short transportation time. Information about the time and place for the follow-up examination is sent via the electronic health record (EHR) and physically by mail to the current address registered in the Civil Registration System. Parents are usually very keen to take their children for follow-up appointments making the risk of missing an appointment low. Any participants who miss an appointment will be contacted by phone to reschedule.

Withdrawal

If a participant chooses to discontinue the follow-up examinations for any reason, the date and reason for drop-out is recorded and the latest examination will be carried forward in the analysis. In case of reoperation, the patients continue with their follow-up examinations and they are included in the 2-year analysis. In case of drop-out before the first follow-up visit the participant will be excluded from the

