analysis. The author will record any protocol violations. Participants are only removed from the study if they decline participation.

Surgical technique and post-operative regime

The preoperative investigations are the same as for operations with a conventional metal implant. They consist of clinical history, physical examination and radiographs in anterior-posterior (AP) and mediallateral (ML) plane. All operations will take place at our hospital and will be carried out by one of five experienced orthopedic trauma surgeons. The surgical procedure is almost identical with that of metal ESIN except the exchange to a bioabsorbable implant after dilation of the medullary canal.

The Activa IM-Nail[™] is implanted according to the manufacturer's surgical technique. Operations are performed under general anesthesia together with a peripheral nerve block (PNB) [31]. Prophylactic antibiotics are given in the form of cloxacillin with dose according to the patient's weight. In the case of allergy towards cloxacillin, cefuroxime will be used as an alternative. Patients are in the supine position with the injured arm on a radiolucent arm table. One incision is made over the radial aspect of the distal radius taking care not to harm the dorsal branch of the superficial radial nerve. Another incision is made over the radial aspect of the proximal ulna. The customized instrumentation for the Activa IM-Nail[™] is used. The cortical bone is opened using an awl and an appropriate size dilator is used. The dilator is replaced with the appropriate size bioabsorbable nail under image intensification to the desired depth and the implant is cut flush with the cortical surface. Wounds are closed using absorbable sutures and dressed. The injured arm is put in an above elbow posterior splint. Post-operative radiographs are taken. The patient is discharged when the effect of the PNB has worn of and the child is well, either on the same day or day after surgery. No formalized physiotherapy or rehabilitation is given beside oral and written information on exercises.

Risks, side effects and disadvantages

Based on previous studies using the Activa IM-Nail[™] [7] we predict that the risk of side effects is comparable or less than those seen with metal ESIN.

Infection

Any surgery caries the risk of infection, however previous studies have shown close to no infection risk [3,32] with the ESIN procedure.

Nerve complications

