Studies have shown a 5% risk of nerve injury [32], however all cases had spontaneous recovery of nerve function.

Extra visits to the outpatient clinic

We follow all patients with six visits to the outpatient clinic. This is three more than with standard treatment and might be viewed as a disadvantage.

Radiation

Three extra radiographs are obtained during outpatient visits. A radiograph of an extremity leads to a radiation dose of less than 0.001 mSv and compares to 3 hours of background radiation. Three extra radiographs is far below the threshold of 0.1 mSv.

MRI

Two years after surgery an MRI is performed. We follow a special MRI-protocol without the need for sedation or anesthesia.

Variables

At recruitment baseline data will be collected:

- Demographic data (age, gender, handedness, height and weight)
- Injury data (date and time, left or right arm, location, activity, mechanism, open or closed fracture, diagnosis code, indication for surgery)
- Historical data (metabolic disease, medication, other systemic illness)

After surgery, operative data is collected (date and time of surgery, operative time, closed or open reduction, any complications).

During follow-up in the outpatient clinic data will be collected on:

- Pain (Faces Pain Scale Revised) or VAS according to child's age
- Use of pain medication
- Wound appearance (visible signs of infection)
- Neurovascular status
- Bilateral elbow and forearm range of motion (ROM) measured in degrees by goniometer
- Forearm radiographs in AP and ML planes (Radiographic Union Score)

2 years following surgery MRI findings (absorption of the nail, activity at fracture site, soft-tissue reactions) will be collected.

Outcomes

The primary objective is quantified using the Radiographic Union Scale (RUS) [33] based on degree of callus formation and visibility of fracture line on AP and ML plain radiographs. We define established healing as a RUS of > 9.

Secondary objectives are described as absolute risk of refracture, time to established healing (weeks), pain (Faces Pain Scale – Revised (FPS-R) or visual analogue scale (VAS)), elbow and forearm range of motion (in degrees), visible signs of infection, neurovascular complications and any reoperation. MRI findings (absorption of the nail, activity at fracture site, soft-tissue reactions) after 2 years are described.

The Radiographic Union Score

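### Operated children who drop out before the 2-week visit are excluded from the analysis with no safety exception, so recorded early complications can fall out of the reported absolute risk

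*Combined protocol and SAP*

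**What the plan says.** The rule is in the Withdrawal section: "In case of drop-out before the first follow-up visit the participant will be excluded from the" analysis (the sentence ends on the next page). The Follow-up section sets the visits: "Outpatient visits are scheduled at 2 and 6 weeks, 3 and 6 months and 1 and 2 years following surgery". Drop-out before the first visit therefore means before the 2-week visit.

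For later drop-outs, the same section records the date and reason and carries the latest examination forward. Reoperated patients who continue follow-up stay in the 2-year analysis. It then adds: "Participants are only removed from the study if they decline participation".

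On safety, Study design defines the cohort as "children with diaphyseal forearm fractures (cohort) operated with BIN (exposure) and report radiological healing" and gives as one aim "calculating absolute risk of adverse events based on the exposure in our cohort". The secondary objectives include to "calculate refracture rate and any other complications up to two years following surgery". Under Variables: "After surgery, operative data is collected (date and time of surgery, operative time, closed or open reduction, any complications". Statistics promises descriptive counts of drop-outs and complications and names no analysis population for safety.

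**The concern.** Exposure, and with it the period at risk, begins at the operation. A rule that makes entry to the analysis depend on attending a visit two weeks later is reasonable for outcomes that exist only if the child is examined: the radiographic union score, pain and range of motion. It does not suit complications. An operative complication is recorded at surgery, and an early reoperation at the hospital would be in the health record. If the family then stops attending, the rule takes the child out of both numerator and denominator.

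At stake is the safety description. The Perspective section gives evaluation of the implant's clinical safety as one purpose of this pilot before the randomised trial. With 30 children, whether the report shows no complication or one can rest on a single child.

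**Working it through.** **Step 1: when risk starts and what is known before week 2.** Study design ties the adverse-event risk to being operated with the nail, and the secondary objective counts complications from surgery. Variables collects operative complications before any outpatient visit. The Hospital records section seeks consent to read entries on visits, admission and operation until the project ends. Safety information on an operated child can thus exist without any visit.

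**Step 2: does anything keep these children in the complication counts?**
- Carrying the latest examination forward does not, because they have no follow-up examination.
- The reoperation sentence covers patients who continue follow-up, not a child who is reoperated and then leaves.
- Statistics defines no safety population.
- Reporting the number of drop-outs shows that children are missing, but not what happened to them.

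**Step 3: illustration of size.** The plan gives no figure to reproduce: the size of 30 is stated without a precision target or drop-out rate. The early drop-out counts below (1 to 3 of 30) are assumptions. Intervals are exact (Clopper-Pearson) 95%.

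| Operated children who have an event and leave before week 2 | All operated children | Under the rule |
|---|---|---|
| 1 | 1/30 = 3.3% (0.1 to 17.2) | 0/29 = 0% (0 to 11.9) |
| 2 | 2/30 = 6.7% (0.8 to 22.1) | 0/28 = 0% (0 to 12.3) |

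Both rows assume no other child has an event.

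**Step 4: how likely is a hidden event?** The protocol's section on nerve complications cites a 5% risk.
- Expected cases in 30: 30 × 0.05 = 1.5.
- Probability of at least one case: 1 − 0.95^30 = 78.5%.
- If leaving is unrelated to injury, the probability that at least one of k excluded children had a nerve injury is 1 − 0.95^k: 5.0% for k = 1, 9.8% for k = 2 and 14.3% for k = 3.

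In that unrelated case the expected proportion among the remaining children is unbiased, although a recorded event can still be lost. If a bad early course prompts families to leave, the probabilities are higher and the reported risk is biased downwards. The documents do not say which applies.

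**The case against.** The sentence may have been written only as the complement of the carry-forward rule: with no examination, nothing can be carried forward. On that reading it was never meant to govern safety, and the plan does not say outright that operative complications are discarded. This is a fair account of the likely intent. But the rule speaks of the analysis without limit, and an analyst following it would drop the child from every table.

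Several limits stand.
- Consent is asked for by the day before surgery, so some early drop-outs may never have received the nail. Excluding them is right for a cohort defined by exposure.
- Wound and neurovascular status are collected at outpatient visits. A deficit or infection that appears after discharge in a child who never returns may go unrecorded under any rule. The clearest loss caused by this rule is the complication recorded at operation.
- Children unable to attend follow-up are ineligible, missed appointments lead to a telephone call, and drop-outs are dated and given a reason. Early losses should be few and visible.

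A reader might also infer that the rule contradicts the sentence "Participants are only removed from the study if they decline participation". The documents do not support that: a child can remain in the study, be counted as a drop-out and still be left out of an analysis. The difference needs stating, but the two sentences can both hold.

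**Conclusion.** The point holds for children already operated with the nail. As written, the rule can remove recorded operative complications, and early complications or reoperations traceable in the health record, from an absolute risk that the study itself bases on the operation. Each hidden event costs about 3 percentage points (1/30 = 3.3%). The intervals overlap widely, and neither a hypothesis test nor the definition of the healing endpoint is affected. What changes is the safety description.

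A reader might go further and conclude that the reported complication risk would be about half the true one. That needs an assumed pattern, namely two events with one of those two children leaving (2/30 = 6.7% against 1/29 = 3.4%). The documents give neither a drop-out rate nor any evidence that early leaving follows a bad course. They support the statement that events can be lost, not that they will be, nor any particular size of bias.

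**What to change.** In Withdrawal and Statistics:
1. Limit the exclusion to outcomes that need a follow-up examination (radiographic union score, pain, range of motion).
2. Report operative and early complications and reoperations in all children in whom the nail was implanted or attempted, counted from surgery whether or not a visit took place. Use the operative record and the consented health-record access, unless that consent is withdrawn. Children who withdraw before surgery stay excluded.
3. For two-year refracture and complication risk, state how many children have complete follow-up or record ascertainment. Otherwise adding children without visits to the denominator would silently count them as event-free and could itself understate the risk.
4. State that exclusion from an analysis differs from removal from the study.

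The cost is a few sentences and a record check for a few children, with no extra visits or participants. The reported complication risk may become slightly less favourable.

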To quantify pain in children age 8 and above we will use a visual analogue scale (VAS) (Figure 2). VAS has been extensively investigated in quantifying pain in older children [40,41]. The child is asked to put a mark on the line corresponding to the child's pain at that moment. A mark to the far left equals no pain and a mark to the far right equals worst possible pain. The line is 10 cm long and the child's mark is measured from left to right in cm with one decimal e.g. 3.4 cm equaling a VAS of 3.4. If the child cannot cooperate to using VAS, FPS-R is used instead.

Figure 2 - Visual analogue scale (VAS) for quantifying pain in children age 8 and above.

Bias

We strive to minimize bias in our study. Displaced forearm fractures do not go unnoticed. A strict protocol for referrals for treatment are in place in Denmark. All eligible patients referred to Herlev and Gentofte University Hospital will be asked to participate in the study. We speculate that by enrolling 30 participants the cohort will be representative of the background population. We speculate that these efforts will limit

selection bias. Efforts described in the follow-up section reduce the risk of loss to follow-up. Overall, we find a low risk of bias in our study for the chosen study design and size.

Study size

The surgical procedure for the Activa IM-Nail[™] resembles that of TEN very much and performing surgeons are all experienced traumatologists. All surgeons will be thoroughly introduced to the procedure, the instruments and the implants, thereby minimizing learning curve phenomenon. We predict that 30 participants will be sufficient in establishing the basis for planning a randomized trial.

Statistics

Data will be analyzed using SPSS (SPSS, Chicago, IL, USA). Descriptive statistics will be used to present the patient-related data, number of dropouts, radiological outcome and number of complications (categorical variables). Age and functional outcome (continuous variables) are expected to be expressed as medians with interquartile ranges. Changes in functional outcome between measurements are expected to be analyzed using Friedman test for related non-parametric data. A p-value of <0.05 is regarded as being significant.

Discussion

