Consent gives the person responsible for the trial and the relevant authorities direct access to obtain information in the patient's medical record for the purpose of carrying out the project as well as for control purposes.

Data security

The patient's hospital records are stored securely in the hospital's EHR (Epic Systems Corporation, Verona, Wisconsin, USA).

The project's Electronic Case Report Form (eCRF) is stored securely using Research Electronic Data Capture (RedCAP, Vanderbilt University, USA).

Radiographs and MRIs are stored in the hospital's Picture archiving and communication system (PACS).

The project complies with the EU's General Data Protection Regulation (GDPR) according to the Danish law on data protection *Databeskyttelsesloven* and *Databeskyttelsesforordningen*.

Publication

The study will be reported to ClinicalTrials.gov before trial initiation.

The results, both positive, negative and inconclusive, will be sent for submission in a peer reviewed international orthopedic journal, and the results will be presented at national and international scientific meetings. Reporting will adhere to the STROBE guidelines for cohort studies [30].

Perspective

If proven safe and effective, the use of BIN would deem hardware removal unnecessary and relieve the child of further surgery and reduce the healthcare costs.

This study is a pilot for a randomized controlled trial comparing the Activa IM-Nail[™] (Bioretec Ltd., [name]) to the Titanium Elastic Nail System (TEN) (Depuy Synthes, Raynham, Massachusetts, USA) which is currently used for pediatric forearm fractures in our hospital. This pilot study will diminish any learning curve, evaluate the clinical safety of the implant, and test the recruiting and follow-up of patients before embarking on the RCT.

Disclosures and economy

The initiative for this study has been taken solely by the authors.

The authors and affiliated colleagues have not received any financial payments or other benefits from any commercial entity related to the subject of this study. The authors declare that they have no conflict of interest.

Participants do not receive any economic benefits or gifts from the participation in this project.

Literature

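### Complication risks from 30 children are planned without intervals, so a zero count would look more reassuring than the data allow

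*Combined protocol and SAP*

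**What the plan says.** Safety appears in several places in the protocol:

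- Perspective gives the pilot's purposes: "This pilot study will diminish any learning curve, evaluate the clinical safety of the implant, and test the recruiting and follow-up of patients".
- Study design justifies the cohort design partly by "calculating absolute risk of adverse events based on the exposure in our cohort". Outcomes also lists an absolute risk of refracture, together with infection signs, neurovascular complications and any reoperation.
- Statistics presents complications descriptively, as "number of complications". It mentions no confidence interval.
- Study size gives one reason for the number: "We predict that 30 participants will be sufficient in establishing the basis for planning a randomized trial".
- The risk section, under Nerve complications, cites one rate: "Studies have shown a 5% risk of nerve injury". The same sentence adds that every case recovered.
- Withdrawal removes from the analysis any participant who drops out before the first follow-up visit. Variables records operative complications directly after surgery, which is before that visit.
- Ethics sets the only numeric safety limit, a refracture rate above 25%, and an interim look six months after the last recruitment.

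**The concern.** An absolute risk estimated from 30 children is very imprecise, and the plan does not ask for that imprecision to be shown. The case that matters is a zero count. Reported as planned, it becomes an absolute risk of 0%, with nothing beside it to show which true risks remain possible. Safety is one of the pilot's stated purposes before a randomised trial in children, so those deciding on that trial would be reading this number.

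The denominator raises a second, smaller issue. A perioperative complication in a child who leaves before the two-week visit is recorded, but the Withdrawal rule could take that child, and the event, out of the reported risk.

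**Working it through.** **The plan's own figure.** The 30 comes with no event rate, precision target, margin or power, so there is no calculation to reproduce. What can be checked is what 30 children deliver.

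**Inputs.** n = 30 (Study size). An illustrative risk of 5% (Nerve complications). Other risks are chosen here to show the range. The documents give no dropout rate; 10% and 20% (n = 27 and 24) are assumptions.

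**Step 1: chance of no event.** P(0) = (1 − p)^n.

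- p = 5%, n = 30: 0.95^30 = 0.215
- p = 5%, n = 27: 0.95^27 = 0.250
- p = 5%, n = 24: 0.95^24 = 0.292
- p = 10%, n = 30: 0.90^30 = 0.042

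At 5% and n = 30, zero is common but is not the likeliest result: P(0) = 0.215, P(1) = 0.339, P(2) = 0.259.

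**Step 2: chance of at least one event in 30.** 1 − (1 − p)^30.

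- p = 1%: 26%
- p = 2%: 45%
- p = 5%: 79%
- p = 10%: 96%
- p = 20%: 99.9%

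**Step 3: exact two-sided 95% (Clopper-Pearson) intervals.** For x events, the lower limit is the 2.5% point of Beta(x, n − x + 1) and the upper limit is the 97.5% point of Beta(x + 1, n − x). For x = 0 the upper limit reduces to 1 − 0.025^(1/n).

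- 0 of 30 (0%): 0 to 11.6%, from 1 − 0.025^(1/30) = 0.116
- 1 of 30 (3.3%): 0.1 to 17.2%
- 2 of 30 (6.7%): 0.8 to 22.1%
- 3 of 30 (10%): 2.1 to 26.5%
- With the assumed dropout, 0 of 27 gives an upper limit of 12.8% and 0 of 24 gives 14.2%.

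For scale, a zero count would need ln(0.025)/ln(0.95) = 71.9, so 72 children, to bring the two-sided upper limit down to 5%.

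**Step 4: the denominator.** Suppose the only complication is perioperative and occurs in a child who leaves before the first visit. Over all children operated the result is 1 of 30, or 3.3% (0.1 to 17.2%). With the Withdrawal rule applied it becomes 0 of 29, with an upper limit of 1 − 0.025^(1/29) = 0.119. The recorded event has disappeared.

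**The case against.** The strongest reply is that this is a descriptive pilot and claims little. Its only hypothesis is radiological healing at three months. The number 30 is justified only as a basis for planning a trial, no decision rule depends on a nerve-injury rate, and safety oversight exists through the interim analysis and the refracture limit. Adding intervals changes no estimate and no planned decision. All of this stands, and it is why the point is minor.

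Four stronger readings are tempting, and the documents do not support them:

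- *The pilot sets out to show safety equal to or better than metal nails.* The sentence "we predict that the risk of side effects is comparable or less than those seen with metal ESIN" is a prior expectation, introduced as based on previous studies. The comparison with metal nails is left to the later randomised trial (Abstract, Perspective).
- *Only raw counts will be reported.* Study design and Outcomes also plan absolute risks. The gap is that no interval goes with them.
- *The 5% is the benchmark for this implant.* The sentence names neither this implant nor metal nails, all cases recovered, and the cited study's title covers both invasive and non-invasive treatment. The 5% is an illustration only.
- *Thirty children are too few for any safety signal.* At a true risk of 10% or more, at least one event is very likely to be seen.

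Being descriptive is not a reason to leave uncertainty out, however. A risk offered as an evaluation of safety needs its interval, whether or not a comparison is made.

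**Conclusion.** The concern holds as a minor reporting gap. The plan intends to evaluate safety and to calculate absolute risks, but Statistics provides neither an interval nor a statement of what 30 children can exclude. A zero count leaves true risks of up to 11.6% possible (two-sided 95%), and at an illustrative 5% risk it would occur 21% of the time.

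These figures assume 30 independent children, each counted once per complication, all observed for the event. Fewer evaluable children widen the limits, as shown for the assumed dropout. How often the Withdrawal rule would remove a recorded event cannot be estimated from the documents; the protocol expects few losses. The primary healing hypothesis is unaffected, and nothing here shows that 30 is the wrong size for a pilot.

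**What to change.** - **Statistics:** report each complication as the number of children with at least one event over all children operated, with an exact Clopper-Pearson two-sided 95% interval, including when the count is zero.
- **Withdrawal:** state that, for complications, the exclusion of dropouts before the first visit does not apply. Because this denominator treats a child lost later as event-free from then on, give the number followed at each visit beside the risks.
- **Study size and Perspective:** limit the safety aim to detecting fairly frequent complications. With 30 children, at least one event is seen with 96% probability at a 10% risk, and 0 of 30 excludes only risks above about 12% (two-sided 95%). Use the same two-sided convention in text and table.

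The cost is a few sentences and an extra column in the complications table, with no added patients, visits or data. The downside is a more modest safety statement.
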